5 STUDY OBJECTIVES

5.1 Primary Objective

To evaluate the efficacy of VX-150 for the treatment of pain caused by small fiber neuropathy

5.2 Secondary Objectives

- To evaluate the safety and tolerability of VX-150
- To evaluate the pharmacokinetics (PK) of VRT-1207355 and the metabolite VRT-1268114

6 STUDY ENDPOINTS

[figure not shown]
6.1 Efficacy Endpoints

6.1.1 Primary Efficacy Endpoint

Change from baseline in the weekly average of daily pain intensity on the 11-point numeric rating scale (NRS), as reported in the daily diary, at Week 6

6.1.2 Secondary Efficacy Endpoints

- Proportion of subjects with $\geq 30\%$ reduction in the weekly average of daily pain intensity on the 11-point NRS, as reported in the daily diary, at Week 6
- Proportion of subjects with $\geq 50\%$ reduction in the weekly average of daily pain intensity on the 11-point NRS, as reported in the daily diary, at Week 6
- Change from baseline in the Daily Sleep Interference Scale (DSIS) at Week 6
- Proportion of subjects categorized as improved at Week 6 on the patient global impression of change (PGIC) assessment
- Change from baseline in pain intensity on the 11-point NRS, as reported at study visits, at Week 6

6.2 Safety Endpoints

- Safety and tolerability based on the Columbia Suicide Severity Rating Scale (C-SSRS), incidence and type of AEs, changes from baseline in clinically significant laboratory test results, vital signs, and ECGs at each visit

7 STUDY DESIGN

7.1 Overall Design

This is a Phase 2, randomized, double-blind, placebo-controlled, parallel-group, multicenter study ([Figure 7-1](#)). Up to approximately 114 subjects with small fiber neuropathy will be randomized 1:1 to VX-150 or placebo.

[figure not shown]
This study will include:

- A 7-day Run-in Period to establish the baseline NRS pain score
- A 6-week Treatment Period

- A 28-day Safety Follow-up

Figure 7-1 VX16-150-102 Study Design

D: Day; qd: daily; W: Week

7.2 Sample Size and Power

The primary efficacy endpoint is the change from baseline in the weekly average of daily pain intensity on the 11-point NRS, as reported in the daily diary, at Week 6. The primary analysis of the primary efficacy endpoint will be a within-group treatment comparison in the VX-150 treatment group. The 95% CI for the within-group change will be used to evaluate if there is any significant change from baseline (within-group change against 0). Additional analyses will include an evaluation of this within-group change against 0.8, an expected change from the placebo group, and a 95% CI for the between-group comparison of change from baseline.

Assuming a within-group change of 0.8 for placebo and a between-group treatment difference of 1.25, the expected within-group change for VX-150 is 2.05. With an SD of 2.08, the power for the 95% CI for the within-group change to rule out 0 or 0.8 is summarized in for 25, 35, or 45 evaluable subjects per group. The power for the 95% CI for the between-group treatment difference to rule out 0 is also provided. In order to allow for withdrawal of up to 20% of randomized subjects over 6 weeks of treatment, the study will enroll and randomize a minimum of approximately 62 subjects (25 evaluable subjects per group) and up to approximately 114 subjects (45 evaluable subjects per group) in total.

Table 7-2 Power for the 95% Confidence Intervals for Within- and Between-group Changes

Number of Evaluable Subjects Per Group	Power for the 95% CI for the Within-group Change to Rule out 0	Power for the 95% CI for the Within-group Change to Rule Out 0.8	Power for the 95% CI for the Between-group Treatment Difference to Rule Out 0
25	> 99%	82%	55%
35	> 99%	93%	70%
45	> 99%	98%	81%

7.3 Randomization

Up to approximately 114 subjects with small fiber neuropathy will be randomized 1:1 to VX-150 or placebo. Randomization will be stratified by sex and diagnosis of diabetes. Subjects with diabetes will not exceed approximately 60% of the total number of subjects. Subjects with diabetes and HbA1c $\geq 8\%$ and $< 11\%$ at screening will not exceed approximately 20% of the total number of subjects.

An interactive web response system (IWRS) will be used to assign subjects to treatment. The randomization code will be produced by Vertex Biostatistics or a qualified randomization vendor. The Vertex study biostatistician will review and approve the production of the final randomization list, which will be reviewed and approved by a designated unblinded biostatistician who is not a member of the study execution team (SET).

7.4 Blinding and Unblinding

This will be a double-blind study.

7.4.1 Blinding

All study personnel will be blinded to subject treatment assignments except for the following individuals:

- Any site personnel for whom this information is important to ensure the safety of the subject in the event of a life-threatening medical emergency
- Any site personnel for whom this information is important to ensure the safety of the subject and the fetus in the event of a pregnancy
- An unblinded pharmacist at the contract research organization (CRO) for dispensing study drug
- Vertex Global Patient Safety (GPS) and Regulatory Affairs personnel to satisfy serious adverse event (SAE) processing and reporting regulations
- External vendor (unblinded) statistician preparing the final (production) randomization list who is not part of the study team
- Vertex IXRS Management for IXRS oversight and system administration
- Vertex Clinical Supply Chain
- The bioanalytical laboratory/vendor personnel managed by Vertex Bioanalysis

Vertex medical monitor may, for matters relating to safety concerns, unblind individual subjects at any time.

A Vertex Bioanalysis Representative will be unblinded to allow real time review of bioanalytical data. This individual, however, will not be a member of the SET, and will not interact with the clinical research unit (CRU) or study personnel.

In addition, a Vertex Clinical Pharmacologist will be partially unblinded to help in management of the PK workspace and ensure that only the blinded PK data set is being provided for preliminary analysis. This individual, however, will not be a member of the

SET, and will not interact with the CRU or study personnel. Masked IDs will be used for these analyses.

7.4.2 Unblinding

At the initiation of the study, the study site will be instructed on the method for breaking the blind. The unblinding method will be either a manual or electronic process.

Unblinding of the individual subject's treatment by the investigator will be limited to medical emergencies or urgent clinical situations in which knowledge of the subject's study treatment is necessary for clinical management. In such cases, investigators will use their best judgment as to whether to unblind without first attempting to contact the medical monitor to discuss and agree to the need for unblinding. If investigators deem it not necessary to unblind immediately, they will first attempt to contact the medical monitor to discuss and agree to the need for unblinding. If investigators have tried but are unable to reach the medical monitor, they will use their best judgment, based on the nature and urgency of the clinical situation, and may proceed with unblinding without having successfully reached and discussed the situation with the medical monitor.

8 ANALYSIS SETS

Assignment of subjects to analysis sets will be performed before the clinical data lock for the study.

8.1 All Subjects Set

The All Subjects Set is defined as all subjects who have been randomized or have received at least 1 dose of study drug. This analysis set will be used in subject listings and disposition summary table, unless otherwise specified.

8.2 Full Analysis Set

The Full Analysis Set (FAS) is defined as all randomized subjects who have received at least 1 dose of study drug. The FAS is to be used in efficacy analyses in which subjects will be analyzed according to their randomized treatment group and not to the treatment they actually received.

8.3 Safety Set

The Safety Set is defined as all subjects who have received at least 1 dose of study drug. The Safety Set is to be used for all safety analyses in which subjects will be analyzed according to the treatment they received and not according to their randomized treatment group.

9 STATISTICAL ANALYSIS

9.1 General Considerations

The Schedule of Assessments is provided in Section 3 of CSP. The precision standards for reporting safety and efficacy variables are provided in an internal Biometrics document that specifies the programming rules including the precision for derived variables.

All individual subject data, including those derived, for subjects who were randomized or received at least 1 dose of study drug, i.e. All Subjects Set, will be presented in individual subject data listings as described.

Continuous variables will be summarized using the following descriptive summary statistics: the number of subjects (n), mean, standard deviation (SD), standard error (SE), median, minimum value (min), and maximum value (max).

Categorical variables will be summarized using counts and percentages.

Baseline value for the NRS via daily diary and the DSIS will be defined as the average score of at least 4 nonmissing scores from Day -7 to Day -1. For all other variables baseline will be defined as the most recent nonmissing measurement collected before the initial administration of study drug unless specified otherwise.

Change (absolute change) from baseline will be calculated as post-baseline value – baseline value unless otherwise specified.

Treatment-emergent (TE) Period will be defined as the time from dosing with study drug until the following time point:

- For enrolled subjects who have a Safety Follow-up Visit: through the Safety Follow-up Visit
- For enrolled subjects who do not have a Safety Follow-up Visit, the earliest of
 - 35 days after the last dose of study drug, or
 - the ETT Visit if that visit is 3 weeks or later following the last dose of study drug (see Section 9.1.5 of CSP)

Unscheduled visits: Unscheduled visit measurements will be included in analysis as follows:

- In scheduled visit windows per specified visit windowing rules.
- In the derivation of baseline/last on-treatment measurements.
- In the derivation of maximum/minimum on-treatment values and maximum/minimum change from baseline values for safety analyses.
- In individual subject data listings as appropriate.

Visit windowing rules: The analysis visit windows for protocol-defined visits are provided in [Appendix A](#).

Incomplete/missing data will not be imputed, unless otherwise specified.

Outliers: No formal statistical analyses will be performed to detect or remedy the presence of statistical outliers, unless specified otherwise.

Multiplicity: No multiplicity adjustment will be performed for hypothesis testing.

9.2 Background Characteristics

9.2.1 Subject Disposition

The number of subjects in the following categories will be summarized overall and by treatment group:

- All Subjects Set
- Randomized
- Full Analysis Set (FAS)
- Safety Set

The number and percentage (based on FAS) of subjects in each of the following disposition categories will be summarized overall and by treatment group:

- Completed treatment
- Prematurely discontinued the treatment and the reason for discontinuation
- Completed study (i.e., completed Safety Follow-up Visit)
- Prematurely discontinued the study and the reason for discontinuation

A listing will be provided for subjects who discontinued treatment or who discontinued study with reasons for discontinuation. A randomization listing of subjects will be provided.

No statistical tests will be carried out to evaluate any baseline imbalance between treatment groups.

9.2.2 Demographics and Baseline Characteristics

Demographics, medical history and baseline characteristics will be summarized overall and by treatment group based on the FAS.

Demographic data will include the following:

- Age (in years)
- Sex (male, female)
- Ethnicity (Hispanic or Latino, not Hispanic or Latino, and not collected per local regulations)
- Race (White, Black or African American, Asian, American Indian or Alaska Native, Native Hawaiian or Other Pacific Islander, not collected per local regulations, Other and Multiracial (if more than 2 races reported from a subject))

Baseline characteristics will include the following:

- Weight (kg)
- Height (cm)
- BMI (kg/m²)

- Diagnosis of diabetes (Yes, No)

Disease characteristics will include the following:

- Pain intensity at baseline as recorded on the NRS
- Daily sleep interference at baseline as recorded on the DSIS

Small fiber neuropathy history will include the following:

- Distribution of the symptoms (stocking/glove distribution, non-length dependent)
- The small fiber neuropathy symptoms have been present for ≥ 3 months (Yes, No)
- Quality of the small fiber neuropathy symptoms (burning, sharp stabbing, throbbing, cold sensation, itch, loss of sensation and other)
- Autonomic features associated with the small fiber neuropathy (Yes, No)

Medical history will be summarized by MedDRA system organ class (SOC) and preferred term (PT).

9.2.3 Prior and Concomitant Medications

Medications taken 28 days before the Screening Visit and up to the Safety Follow-up will be coded and summarized by Preferred Name using the World Health Organization-Drug Dictionary (WHO-DD) for the FAS as frequency tables in 2 parts:

1. Prior medication: Medication that started before the first dose of study drug, regardless of when dosing of the medication ended.
2. Concomitant medication: Medication received at or after the first dose of study drug, medication that was received before initial dosing and continued after initial dosing of study drug, or medication with missing stop date.

Medication that started before the first dose of study drug and continued after the first dose of study drug will be summarized as prior medication and separately as concomitant medication.

If a medication has a completely missing or partially missing start/stop date and it cannot be determined whether it was taken before the first dose date or concomitantly, it will be classified as prior and concomitant.

Details for imputing missing or partial start and/or stop dates of medication are described in [Appendix B](#).

9.2.4 Study Drug Exposure and Study Drug Compliance

Study drug exposure and study drug compliance summaries will be based on the FAS.

Duration of study drug exposure is defined as follows: last dose date – first dose date + 1 day, regardless of any interruption in dosing between the first and the last dose. Duration of study drug exposure expressed in weeks will be summarized by means of descriptive summary statistics and also into the following categories: ≤ 1 weeks, >1 and ≤ 3 weeks, >3 and ≤ 6.5 weeks, and >6.5 weeks.

Dosing compliance rate will be calculated as following:

$100 \times [(\text{total number of tablets dispensed}) - (\text{total number of tablets returned})] / (\text{total number of tablets planned to be taken per day} \times \text{duration of study drug exposure in days})$.

The dosing compliance rate will be summarized descriptively and into the categories of <80%, and $\geq 80\%$.

9.2.5 Important Protocol Deviations

Important protocol deviation (IPD) is a subset of protocol deviations (any change, divergence, or departure from the study design or procedures defined in the protocol) that may significantly impact the completeness, accuracy, and/or reliability of the study data or that may significantly affect a subjects' rights, safety or well-being. IPDs will be identified from the clinical database and/or site deviation log.

A list of categories of IPDs identified for this study is presented in [Appendix E](#).

All IPDs will be summarized descriptively by treatment group and presented in an individual subject data listing.

9.3 Efficacy Analysis

Unless otherwise defined, all efficacy analyses described in this section will be based on the FAS. Subjects will be analyzed according to their randomized treatment assignment.

9.3.1 Analysis of Primary Efficacy Variable

9.3.1.1 Definition of Primary Efficacy Variable

The primary efficacy endpoint is the change from baseline in the weekly average of daily pain intensity on the 11-point NRS, as reported in the daily diary, at Week 6. The weekly average of daily pain intensity will be calculated by averaging the nonmissing daily pain intensity scores in each week. If the count of nonmissing daily pain intensity scores is less than 4 within a week, the weekly average of daily pain intensity will be set to missing.

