The neurological component of the Day 1 complete physical examination includes sensory testing conducted with the bedside sensory testing kit (BSTK). Symptom-directed physical examinations will occur at any time during the study if triggered by AEs or if deemed necessary by the investigator.

With the exception of Day 7, PK samples will be collected at any time during the study visit. On Day 7, 2 PK samples will be collected: 1 sample before the dose of study drug, and 1 sample 1 to 4 hours after the dose of study drug.

Table 3-2 Study VX16-150-102: Run-in Period, Treatment Period, and Safety Follow-up Visit

Event/Assessment	Day -7 (During Screening)	Day 1	Day 7 (± 1 Day)	Week 3 (± 3 Days)	Week 6 (± 3 Days)	ETT Visit ^a	Safety Follow-up Visit 28 (± 7) Days After the Last Dose of Study Drug
11-pt numeric rating scale (NRS) pain score via daily diary ⁱ		Day -7 through	n Week 6 or ETT Vi	sit via daily diary			
11-pt NRS pain score at study visits ^j	X	X	X	X	X	X	X
Daily Sleep Interference Scale (DSIS) ^k		Day -7 through	n Week 6 or ETT Vi	sit via daily diary			
Patient global impression of change (PGIC)		X	X	X	X	X	X
Columbia Suicide Severity Rating Scale (C-SSRS)		X	X	X	X	X	X
Study drug count			X	X	X	X	
Medications review		Cont	inuous from signing	of the ICF through	the Safety Follow-up	Visit	·····
Concomitant treatments and procedures		Cont	inuous from signing	of the ICF through	the Safety Follow-up	Visit	
Adverse events		Cont	inuous from signing	of the ICF through	the Safety Follow-up	Visit	

From Day -7 through Week 6 or ETT Visit, subjects will report their average daily pain during the last 24 hours on the NRS each evening. Subjects will also report their current pain immediately before each administration of rescue medication.

At study visits, subjects will report their average pain during the last 24 hours on the NRS.

From Day -7 through Week 6 or ETT Visit, subjects will report each morning on the previous night's sleep using the DSIS.

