8.1 Inclusion Criteria

- 1. Subject will sign and date an informed consent form (ICF)
- 2. Willing and able to comply with scheduled visits, treatment plan, study restrictions, laboratory tests, contraceptive guidelines, and other study procedures
- 3. Subjects (male and female) will be between the ages of 18 and 80 years, inclusive.
- 4. Body mass index (BMI) of \geq 18.0 kg/m²
- 5. Diagnosis of small fiber neuropathy, as per European Federation Neurological Societies (EFNS)/American Academy of Neurology (AAN) guidelines, with pain for at least 3 months prior to screening
- 6. Reduction below the 5th percentile of sex and age-adjusted normal values in epidermal nerve fiber density on punch skin biopsy at the distal site of the leg performed at screening
- 7. Presence of sural nerve responses
- 8. Average NRS score between ≥ 4 and ≤ 9 reported in the daily diary on Days -7 through -1

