9.4 Study Restrictions

Study restrictions are summarized in Table 9-1.

Table 9-1 Study Restrictions

Restricted	Timing of Restriction		
Medication/Food/Activity ^a	From (minimum)	То	
Other investigational drugs or devices	1 month before first study drug dose, or time determined by local requirements; whichever is longest	Completion of Safety Follow-up Visit assessments	
Sensitive CYP3A substrates	7 days before first study drug dose	Completion of Safety Follow-up Visit assessments	
Medications with potential effects on sodium channel function, including lamotrigine, carbamazepine, oxcarbazepine, mexiletine, amitriptyline, and topical agents	14 days before first study drug dose	Completion of Week 6 or ETT Visit assessments	
Any use of marijuana or marijuana derivatives	14 days before first study drug dose	Completion of Week 6 or ETT Visit assessments	
Capsaicin patch	90 days before first study drug dose	Completion of Week 6 or ETT Visit assessments	
Gabapentin and pregabalin	14 days before first study drug dose	Completion of Week 6 or ETT Visit assessments	
All treatments for pain (as outlined in Section 9.4.1)	14 days before first study drug dose	Completion of Week 6 or ETT Visit assessments	
Vitamin E supplements	7 days before first study drug dose	Completion of Safety Follow-up Visit assessments	

Table 9-1 Study Restrictions

Restricted	Timing of Restriction		
Medication/Food/Activity ^a	From (minimum)	То	
Grapefruit/grapefruit juice,	7 days before first study drug dose	Completion of Week 6 or ETT Visit	
pomelos, star fruit, Seville		assessments	
oranges, marmalade			

^a Refer to the Study Reference Manual for a more complete list of prohibited/restricted medications.

All medications taken from 28 days before screening through the Safety Follow-up Visit will be recorded with indication, route of administration, and start and stop dates of administration. All subjects will be questioned about medications at each study visit.

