9.4.1 Treatments for Pain

- Subjects will abstain from all treatment for neuropathic pain (including medications, supplements, and non-pharmaceutical therapies) from 14 days before the first dose of study drug through the Week 6 Visit (or ETT Visit, if applicable). Subjects taking aspirin for cardiovascular health may remain on their stable dose throughout the study.
- Acetaminophen will be permitted as a pain rescue medication prn throughout the study. Subjects will be permitted to take 500 mg every 4 to 6 hours prn, up to a maximum of 2500 mg in any 24-hour period prn. Subjects will record rescue medication use, and their current pain on the NRS immediately before each administration of rescue medication.
- There are no restrictions on pain treatments between the completion of the Week 6 Visit (or ETT Visit, if applicable) and the Safety Follow-up Visit.

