12.3.1 General Considerations

All individual subject data for all individual subjects randomized or exposed to study drug will be presented in data listings. Continuous data will be summarized using the following descriptive summary statistics: the number of subjects (n), mean, SD, SE, median, minimum value (min), and maximum value (max). Categorical data will be summarized using counts and percentages.

Baseline value for the NRS daily diary scores and the DSIS will be defined as the average score from Day -7 to Day -1. For all other variables baseline will be defined as the most recent non-missing measurement collected before the initial administration of study drug.

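### Inclusion criterion 8 sets no minimum number of run-in diary scores although the SAP baseline needs 4; the SAP should also state that entries after the Week 6 visit do not count

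*SAP*

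**What the plan says.** **Run-in and baseline.** Criterion 8 (Protocol 8.1) requires an average NRS score from 4 to 9, "reported in the daily diary on Days -7 through -1", with no minimum number of entries. The baseline in Protocol 12.3.1 is "defined as the average score from Day -7 to Day -1", again with no minimum. SAP 9.1 is stricter: for the diary NRS and the DSIS, baseline is the "average score of at least 4 nonmissing scores from Day -7 to Day -1". The same section does not impute missing data unless otherwise specified. It keeps the last-nonmissing-value definition of baseline for all other variables. The FAS (SAP 8.2) asks only for randomisation and one dose. The primary MMRM (SAP 9.3.1.2) uses baseline twice: inside the change score and as a covariate.

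**Week 6.** SAP 9.3.1.1 defines the weekly mean: "The weekly average of daily pain intensity will be calculated by averaging the nonmissing daily pain intensity scores in each week". It is set to missing "If the count of nonmissing daily pain intensity scores is less than 4 within a week". SAP Appendix A fixes the Week 6 diary window at Days 36 to 42 and the Week 6 visit target at Day 43. Protocol Table 3-2 allows that visit ±3 days. Its diary footnote says that "subjects will report their average daily pain during the last 24 hours on the NRS each evening". Protocol Table 9-1 ends the pain-treatment restrictions at "Completion of Week 6 or ETT Visit assessments".

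**The concern.** Eligibility and analysis apply different rules to the same seven days. A site can compute an average from one to three entries, find it between 4 and 9, and randomise the subject. Under the SAP that subject has no baseline, hence no change score and no covariate value, and drops out of the primary model at every week. The missing-at-random assumption in SAP 9.3.1.2 does not help, because it is the baseline that is missing and not a post-baseline outcome. The subject has been exposed to study drug and adds nothing to the primary analysis.

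The Week 6 window raises a smaller question. It is tied to study days and not to the visit, and the visible SAP does not say how to treat a diary score entered after an early but in-window visit, when other pain treatment is allowed. A shift common to both arms would cancel in the between-group difference. It would not cancel in the within-group VX-150 change, which is the primary comparison.

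**Working it through.** **1. The plan's own power figures.** Inputs from Protocol 12.1 and SAP 7.2: VX-150 change 2.05, placebo change 0.8, difference 1.25, SD 2.08, two-sided 95% CI. I used noncentral t power. The one-sample noncentrality is δ/(2.08/√n) with n-1 df. The two-sample noncentrality is δ/(2.08√(2/n)) with 2n-2 df.

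| n per group | against 0 | against 0.8 | between groups |
|---|---|---|---|
| 25 | 99.7% | 82.2% | 54.9% |
| 35 | >99.9% | 93.2% | 69.8% |
| 45 | >99.9% | 97.6% | 80.5% |

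These agree with the printed table to within a point.

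**2. Subjects with 1 to 3 run-in scores.** The documents give no diary completion rate. I assume a daily completion probability p, independent by day. Then P(1 to 3 of 7) = Σ C(7,k) p^k (1-p)^(7-k) for k = 1 to 3. At p = 0.85 this is 0.0001 + 0.0012 + 0.0109 = 0.0121. The power columns apply the loss to 45 evaluable per group, so n = 45 × (1 - loss).

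| p | share | of 114 | n per group | between-group power | against 0.8 |
|---|---|---|---|---|---|
| 0.95 | 0.02% | 0.02 | 44.99 | 80.5% | 97.6% |
| 0.85 | 1.2% | 1.4 | 44.46 | 80.0% | 97.5% |
| 0.80 | 3.3% | 3.8 | 43.50 | 79.1% | 97.2% |

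Power against 0 stays above 99.9% in every row.

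**3. Week 6 day count.** The visit may fall on Days 43 ± 3, that is 40 to 46. Days 40, 41 and 42 overlap the diary window of Days 36 to 42. Scores dated up to and including visit day v number min(7, v - 35): 5, 6, then 7 for Days 42 to 46. At p = 0.85 the chance of fewer than 4 scores is 16.5% for Day 40, 4.7% for Day 41 and 1.2% for each later day. With visits assumed evenly spread, the mean is (0.1648 + 0.0473 + 5 × 0.0121)/7 = 3.9%. It is 1.2% when all seven days count.

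**4. What that costs in power.** I assume a correlation of 0.85 between Weeks 5 and 6, through which the MMRM recovers part of the loss L. The variance factor is 1 + [L/(1-L)](1 - 0.85²). It is 1.0034 for L = 0.0121 (n = 44.85, between-group power 80.4%) and 1.0112 for L = 0.0389 (n = 44.50, 80.0%).

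**5. Possible shift in the Week 6 mean.** The documents give no per-score shift, so 1 point is purely illustrative. I count the visit-day evening recall as 8/24 after the visit, also assumed.

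- *Diary ends with the visit-day evening entry.* For a Day 40 visit the shift is (1/3)/5 = 0.07. The average over visit days is (0.067 + 0.056 + 0.048)/7 = 0.024. Power against 0.8 moves from 97.6% to 97.2% or 98.0%, depending on direction.
- *Diary continues to Day 42.* For a Day 40 visit the shift is (2 + 1/3)/7 = 0.33. The average is (2⅓ + 1⅓ + ⅓)/49 = 0.08. Power against 0.8 moves to 95.8% or 98.7%.

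Power against 0 stays above 99.9% in both cases.

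**The case against.** On the run-in, the SAP says that it adds detail to the protocol, and its rule already settles the outcome: fewer than 4 scores means no baseline. The gap arises before randomisation, so it cannot depend on assigned treatment. Criterion 2 already asks for subjects able to follow study procedures. All of this stands, and it is why the matter is minor. It does not remove the loss: the SAP defines what happens to a subject who should not have been randomised under its own rule, and criterion 8 is the place to prevent it.

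On Week 6, a reader might infer that up to 3 of the 7 scores in the primary mean are recorded after the restrictions end. The documents do not support this as the expected case. Table 3-2 collects the diary from Day -7 to Week 6 or the early-termination visit. Table 9-1 uses the same pairing for the end of restrictions, where it can only mean the visit, and Protocol 9.4.1 names the Week 6 visit outright. Read together, these end the diary at the visit. At most the visit-day evening entry then follows it, and its 24-hour recall partly precedes the visit. Protocol 11.5 is shorter but does not say that entries go on after the visit. This objection largely stands. What remains is that no sentence states the cut-off.

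**Conclusion.** The run-in mismatch holds on the text. Its size rests on an assumed completion rate: 1.2% of subjects, about 1.4 of 114, at 85%, within a range of 0.02% to 3.3% for 95% to 80%. Between-group power falls by about half a point at 85% and by about 1.4 points at 80% (80.5% to 79.1%). It is a cheap alignment, not a threat to the trial.

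The Week 6 point is a safeguard that matters only if the diary continued after an early visit. Any figure for the shift in the within-group change depends on an assumed per-score shift, so none of those in the check is a bound. A reader should not infer that the primary comparison with 0 is at risk; it is unaffected in practice.

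**What to change.** **Protocol 8.1, criterion 8.** Add a requirement for at least 4 of 7 diary scores on Days -7 to -1, matching SAP 9.1. Cost: one phrase. The few subjects concerned (about 1.2% at 85% completion) become screen failures, so their data are not recovered. The change helps only while screening is open.

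**SAP Appendix A, Week 6 diary window.** State that entries dated after the day of the Week 6 visit do not enter the Week 6 mean. Visit-day entries stay in. Cost: one sentence before database lock. If the diary ended at the visit, the rule removes nothing. If it continued, about 3.9% of completers would lack a Week 6 value against 1.2% (assumed 85% completion, evenly spread visits), and between-group power would go from 80.4% to about 80.0% under the correlation assumed above.
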